8.3.2 Classification of an Adverse Event

8.3.2.1 Severity of Event

Event severity will be assigned according to the Investigator's (or designee's) assessment.

Severity Grade for Parameters Not Identified in the Grading Table:

The functional table (

Table 12) should be used to grade the severity of an AE that is not specifically identified in the grading table. In addition, all deaths related to an AE are to be classified as Grade 5.

Table 12 Severity Grade for Parameters

PARAMETER	GRADE 1 MILD	GRADE 2 MODERATE	GRADE 3 SEVERE	GRADE 4 POTENTIALLY LIFE-THREATENING

Clinical adverse event NOT identified elsewhere in the grading table	Mild symptoms causing no or minimal interference with usual social & functional activities with intervention not indicated	Moderate symptoms causing greater than minimal interference with usual social & functional activities with intervention indicated	Severe symptoms causing inability to perform usual social & functional activities with intervention or hospitalization indicated	Potentially life-threatening symptoms causing inability to perform basic self-care functions with intervention indicated to prevent permanent impairment, persistent disability, or death
--	--	---	--	---

8.3.2.2 *Relationship to Study INTERVENTION*

Attribution/Assessment of Causality is a determination that describes the relationship or association of the study product with an adverse event.

This assessment of causality or relationship of AEs to the study product is provided by the Investigator and is determined by 1) temporal relationship of the event to the administration of study product, 2) whether an alternative etiology has been identified, and 3) biological plausibility. Causality must be assessed separately for each study product.

The causality assessment categories that will be used for this study are described below.

1. Causality assessments that are considered not related to study product:

a. Not related:

The event is related to an etiology other than the study product (the alternative etiology must be documented in the participant's medical record).

If an SAE is considered "unrelated" to study product, the Investigator should offer his/her clinical opinion as to what factor(s), agent(s), or process(s) were the likely causative mechanism for the event.

2. Causality assessments that are considered related to study product:

a. Possible:

There is an association between the event and the administration of the study product and there is a plausible mechanism for the event to be related to study product; but there may also be alternative etiology, such as characteristics of the participant's clinical status or underlying disease.

b. Probable:

There is an association between the event and the administration of study product, a plausible mechanism for the event to be related to the study product, and the event could not be reasonably explained by known characteristics of the participant's clinical status or an alternative etiology is not apparent.

c. Definite:

There is an association between the event and the administration of study product; a plausible mechanism for the event to be related to the study product, causes other than the study product have been ruled out, and/or the event re-appeared on re-exposure to the study product.

8.3.2.3 *Expectedness*

The study PI (or designee) will be responsible for determining whether an adverse event (AE) is expected or unexpected. An AE will be considered unexpected if the nature, severity, or frequency of the event is not consistent with the risk information previously described for the study intervention or is not listed in the most current IBs for the study intervention.

8.3.3 *Time Period and Frequency for Event Assessment and Follow-Up*

The occurrence of an adverse event (AE) or serious adverse event (SAE) may come to the attention of study personnel during study visits and interviews of a study participant presenting for medical care, or upon review of medical record.

All AEs including local and systemic reactions not meeting the criteria for SAEs will be captured in the research record on the appropriate form. Information collected includes:

- Event description,
- Time of onset,
- Study PI's (or designee's) assessment of severity, relationship to study product and expectedness,
- Time of resolution/stabilization of the event.

All AEs occurring while on study must be documented appropriately regardless of relationship. All study- related AEs will be followed to adequate resolution.

Any medical condition that is present at the time that the participant is screened will be considered baseline and not reported as an AE. However, if the study participant's condition deteriorates at any time during the study, it will be recorded as an AE.

Changes in the severity of an AE will be documented to allow an assessment of the duration of the event at each level of severity to be performed. AEs characterized as intermittent require documentation of onset and duration of each episode.

The study research coordinator will record all reportable events with start dates occurring any time on or after the enrollment visit until 7 days (for non-serious AEs) or 30 days (for SAEs) after the last day of study participation. At each study visit, the research coordinator will inquire about the occurrence of AE/SAEs since the last visit. Vaccine-related and/or reportable events will be followed for outcome information until resolution or stabilization.

Clinical Laboratory Changes:

Safety laboratory assessments will be carried out locally at UNC and evaluated by the Investigator (or designee) to ensure participant safety. The Investigator (or designee) is responsible for reviewing the results of all laboratory tests as they become available.

- Laboratory values that fall outside of a clinically accepted reference range or differ significantly from previous values must be evaluated for clinical significance by the Investigator (or designee). The Investigator (or designee) may repeat the laboratory test or request additional tests to verify the results of the original laboratory tests.
- If the Investigator (or designee) determines the laboratory value is an abnormal change from baseline and is of clinical significance for that participant, it is considered an AE.
- Generally, Grade 1 and Grade 2 laboratory findings need not be reported as AEs unless deemed clinically significant by the Investigator (or designee).
- Consistent with the DAIDS designation of Grade 3 events as severe or medically significant and Grade 4 events as life-threatening, Grade 3 and Grade 4 laboratory findings should be reported as AEs or SAEs, as appropriate.
- The test result or finding should be reported as the AE. Such laboratory values should generally be recorded as “increased” or “decreased” (e.g., change from baseline potassium of 5.0 to 3.5 mEq/L = potassium decreased).

The study PI (or designee) is responsible for appropriate reporting of AEs to the regulatory authorities. The study PI (or designee) will also report all suspected unexpected serious adverse reactions. The study PI (or designee) must report suspected unexpected serious adverse reactions to the FDA if applicable and to the UNC IRB, per the UNC IRB reporting requirements.

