Occurrence of at least one \geq Grade 3 Adverse Event (AE) including signs/symptoms, lab toxicities, and/or clinical events, that is possibly, probably or definitely related to study treatment any time from the first day of treatment through 28 days following vaccination.

Secondary Endpoint: Safety

Occurrence of any \geq Grade 1 AE including signs/symptoms, lab toxicities, and/or clinical events, that is possibly, probably, or definitely related to study treatment any time from the first day of treatment through Day 168 (Week 24) following vaccination.

Safety data will include local and systemic signs and symptoms, laboratory measures of safety/toxicity, and all adverse and serious adverse events. Safety data will be routinely collected throughout the duration of the study.

NOTE: The occurrence of a Grade 3 elevated blood pressure during a study-related leukapheresis that resolves following completion of the procedure will not be included as a primary safety endpoint.

Secondary Endpoints: Immunogenicity

Relative change in magnitude of T cell responses to HIV-1 conserved regions from pre-vaccination (Day 0) to post-vaccination at Day 7 and Day 14.

Change in breadth of T cell responses targeting HIV conserved regions from pre-vaccination (Day 0) to post-vaccination at Day 28.

Study Population: HIV-infected men and women ≥ 18 and ≤ 65 years of age with viral suppression on ART as measured on standard HIV RNA assays. Eligible participants must have a CD4 cell count ≥ 350 cells/mm³ at screening.

Phase: Phase 1

Description of Facilities Enrolling Participants: Single site - The University of North Carolina, Chapel Hill, North Carolina, USA.

Description of Study Intervention: This is a double blind, randomized, placebo-controlled, parallel design, study in which 24 HIV-infected participants with durable viral suppression will be randomly assigned to receive vaccination with MVA.tHIVconsV3 (M3), MVA.tHIVconsV4 (M4), M3+M4 combined, or placebo.

Participants will be randomized 7:7:7:3 to one of four study arms, and receive study treatment or placebo at Day 0.

Study Schema

Arm	N	Day	Treatment	Dose (pfu)	Route
1	7	0	M3	2×10^8	IM
2	7	0	M4	2×10^8	IM
3	7	0	M3+M4	1×10^8 , each vaccine	IM

[figure not shown]
4	3	0	Placebo (saline)	-	IM
---	---	---	---------------------	---	----

M3 = MVA.tHIVconsv3
M4 = MVA.tHIVconsv4
pfu = plaque forming units
IM = intramuscular

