ART Adherence Assessment: This protocol requires participants take all required doses of ART. Document all missed doses, even if the reason/s for missing the doses are outside the participant's control. Report missed doses to study PI (or designee). Study participation can be terminated if HIV medication is missed.

For the purpose of this study, non-adherence is defined as missing doses for more than two (2) consecutive days or more than four (4) cumulative days in the prior 12 weeks (3 months) prior to screening visit. Assess and document any missed doses while on study and discuss missed ART doses with study PI (or designee). Continuation on study will be contingent on adherence.

Antiretroviral Medication Assessments: During the study, all modifications to the participant's ART regimen, including any ARV interruptions, dose modifications, formulations modifications, starts, and permanent discontinuations since the last study visit or at the study visit must be recorded.

Signs and Symptoms Assessments: At entry, all signs and symptoms, regardless of grade, that occurred within the 30 days before entry must be recorded.

Active solicitation of AEs will be done at every study visit. Post-entry signs and symptoms, Grade ≥ 2 , will be recorded. All signs or symptom, definitely, possibly, or probably related to study interventions will be recorded, regardless of grade. Additionally, all signs and symptoms that lead to a change in study treatment or change in ART or discontinuance of the leukapheresis procedure, regardless of grade, must be recorded.

Diagnoses: After entry, record all diagnoses identified.

Concomitant Medication Assessments: At screening and entry, record all medications taken per medical history guidelines. Thereafter, record all new or discontinued concomitant medications, including prescription, dietary supplements, and over-the-counter medications taken or stopped since the last visit.

Laboratory Studies

CD4⁺/CD8⁺: All study required absolute CD4⁺/CD8⁺ count and percentages must be obtained from a laboratory that possesses a CLIA certification or equivalent. Eligibility will be determined based on a CD4⁺ ≥ 350 at screening.

Plasma HIV-1 RNA: All study required HIV-1 RNA assays must be performed by a laboratory that possesses a CLIA certification or equivalent. Eligibility will be determined based on an HIV-1 RNA value <50 at screening.

Research Assays

Blood will be collected for the following research laboratory evaluations:

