Flu like symptoms	Temperature (fever $>37.7^{\circ}\text{C}$ or 99.9°F)
Sweating	Chills
Diarrhea	Nausea
Dizziness	Myalgia (muscle pain)
Anorexia	Abdominal pain
Syncope	

Study staff will follow new or unresolved vaccine-related AEs to resolution. In general, participants self-reporting any post-injection reaction greater than mild are to be evaluated by the study PI (or designee) within 72 hours after onset, unless the reaction is improving and/or has completely resolved.

Institute appropriate countermeasures, including medical intervention or procedures, if clinically indicated.

8.2.11 *Laboratory Evaluations*

Details of specimen collection are found in the Lab Procedures Manual for this study.

Labs utilized for processing and resulting the clinical evaluations are the UNC McLendon Lab and LabCorp. The study PI (or designee) assesses the results of all clinical laboratory tests to determine continuing eligibility or AE relatedness at specified visits. Lab results or values outside the normal reference range require the investigator (or designee) to determine if the abnormal value is clinically significant and/or related to a study intervention. All confirmed abnormal laboratory values that the investigator deems clinically significant and/or related to a study intervention must be reported as AEs, regardless of grade. Post-entry laboratory values, Grade ≥ 2 , will be recorded. Participants and/or their primary care provider will be informed of any clinically significant laboratory test result or clinical event that occurs throughout the study. Participants will be referred for care when appropriate.

Hematology: Perform hemoglobin, hematocrit, white blood cell count (WBC), differential WBC, absolute neutrophil count (ANC), and platelet count in real time at the local laboratory.

Note: CBC with differential for Leukapheresis procedures:

- A STAT CBC with differential is required prior to each leukapheresis performed at the UNC Apheresis Lab unless results completed within 24 hours of the procedure are available to the Apheresis Lab performing the procedure.
- Leukapheresis procedures performed at a local apheresis collection center require a CBC within 30 days of procedure.

Liver Function Tests: Perform total bilirubin, AST (SGOT), ALT (SGPT), and alkaline phosphatase in real time at the local laboratory.

NOTE: For participants on ritonavir boosted atazanavir, total and direct bilirubin should be measured.

Blood Chemistries

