8.3.4 Adverse Event Reporting

Adverse events will be graded according to the DAIDS Table for Grading the Severity of Adult and Pediatric Adverse Events (DAIDS AE Grading Table), corrected Version 2.1, July 2017, on the DAIDS RSC website at <http://rsc.tech-res.com/clinical-research-sites/safety-reporting/daids-grading-tables>.

The study will monitor participants for adverse events. Toxicities will be characterized in terms including duration, intensity, and time to onset. Safety endpoints will include all adverse experiences, in addition to laboratory safety assessments, and vital signs. All AEs will be recorded on the appropriate study form.

AEs will be recorded in the database if any of the following criteria have been met:

- Study-related Grade ≥ 1 AEs
- Grade ≥ 3 AEs
- Autoimmune-related AEs regardless of grade
- HIV viral loads ≥ 50 copies/mL
- Injection reactions regardless of grade
- AEs that led to a change in study intervention regardless of grade
- AEs meeting SAE definition or EAE (Expedited Adverse Event) reporting requirement

Grade 1 or 2 Toxicity

Participants who develop a Grade 1 or 2 AE or lab toxicity that occurs following a vaccine/placebo injection that is thought to be possibly, probably, or definitely related to the study treatment should be discussed with the study team. Grade 1 or 2 AEs that may be related to the vaccine/placebo injection will be handled according to standard clinical practice and documented.

Grade 3 Toxicity

For participants who develop a Grade 3 AE following the administration of vaccine/placebo judged by the study PI (or designee) to be at least possibly study treatment-related, the protocol team must be notified within 24 hours. Participants experiencing Grade 3 AEs should be followed closely and if the AE does not return to

Grade ≤ 2 within 2 weeks, the study team should again be notified within 24 hours and the SMC will be notified.

For participants who experience a Grade 3 AE judged not related to the study treatment by the investigator, continued study participation is at the discretion of the study PI (or designee) in consultation with the protocol team and SMC.

Grade 4 Toxicity

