Injection Site Erythema or Redness and Injection Site Induration or Swelling will not be considered an AE if there is no interference with usual social and functional activities such that:

- Grade 1 is: 2.5 to < 5 cm in diameter OR 6.25 to < 25 cm² surface area;
- Grade 2 is: ≥ 5 to < 10 cm in diameter OR ≥ 25 to < 100 cm² surface area;
- Grade 3 is: ≥ 10 cm in diameter OR ≥ 100 cm² surface area OR Ulceration OR Secondary infection OR Sterile abscess OR Drainage;
- Grade 4 is: Potentially life-threatening consequences (e.g., abscess, exfoliative dermatitis, necrosis involving dermis or deeper tissue)

Allergic or Hypersensitivity Reactions

Record all allergic and hypersensitivity reactions with both grade severity and attribution. Serious allergic or hypersensitivity reactions (≥ Grade 3) that are deemed possibly related to the study treatment by the study PI (or designee) will be reported to the protocol team and SMC within 24 hours of notification and to the NIH/DAIDS, UNC IRB, FDA, and study product sponsors within 48 hours per their reporting requirements.

Dose Limiting Toxicity (DLT)

- Hematologic dose-limiting toxicity will be defined as any confirmed toxicity ≥ Grade 2, that cannot clearly be attributed to another reversible cause.
- Follow participants per protocol schedule of events until the lab abnormality or toxicity resolves to ≤ Grade 1 or the participant's baseline.

- Non-hematologic dose-limiting toxicity will be defined as any confirmed symptomatic \geq Grade 3, if related (definitely, probably, or possibly) to vaccine/placebo.

Monitoring HIV RNA levels

In the event of viremia of \geq 50 copies/mL the following should occur per standard of care:

- Adherence to ART should be carefully assessed and documented.
- A standard HIV RNA assay should be repeated within 1-4 weeks.
- HIV resistance testing will be performed at the time of drawing a confirmatory sample and as indicated for persistent viremia.
- For HIV RNA confirmed >200 copies/mL on repeat testing, stored samples may be tested for the presence of one or more ARV drugs in the participant's regimen.
- HIV RNA will be repeated every 2 weeks, or sooner as clinically indicated, until <50 copies/mL and the participant can continue on study.

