9.3.8 Safety Analyses

For the safety endpoints, we will describe all study treatment-related AEs through Day 28 (primary endpoint) and the end of study (secondary endpoint). AEs will be coded per the Medical Dictionary for Regulatory Activities (MedDRA). Events prior to treatment (e.g., due to study-related procedure) will be listed separately in an appendix to the final clinical study report. The following tables of AE data will be created to summarize the number and percent of participants who experience at least one event of each of the following types:

- Study treatment-related AEs by severity grade
- All SAEs (this may be a listing if there are few events)
- Study treatment-related SAEs
- Fatal AEs (this may be a listing if there are few events)
- AEs that result in study discontinuation or study treatment discontinuation
- AEs categorized as AESI
- AEs with severity Grade 3 or greater
- Study treatment-related AEs with severity Grade 3 or greater
- All treatment-related AEs with severity Grade 1 or greater

All of these tables will display the number and percent of participants that experience the given event and will display events by System Organ Class (SOC) and Preferred Term (PT). Events will be displayed alphabetically for SOC and in descending order of overall PT incidence within each SOC.

9.3.9 *Tabulation of Individual Participant Data*

Individual participant data will be listed by measure and time point.

9.3.10 *Exploratory Analyses*

Other objectives or exploratory analysis can be grouped into additional immunological measures and virologic measures.

Immunologic measures: Kinetic data will be analyzed by descriptive statistics and graphical displays. Other observed immunologic measurements such as virus inhibition may not be normally distributed or may be partially censored due to assay limits of quantification, and thus, an exact Wilcoxon signed-rank test will be used for within-participant comparisons.

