10.1.6 Safety Oversight

Safety oversight will be under the direction of a Safety Monitoring Committee (SMC) composed of individuals with the appropriate expertise. Members of the SMC are independent from the study conduct and free of conflict of interest.

The SMC advises the study PI and protocol team for this First in Man, Phase I study. The primary responsibility of the SMC is to monitor human subject safety. The SMC considers study-specific data as well as relevant background information about the disease, test agents, and target population under study.

During the trial, the SMC will review:

- Real-time and cumulative safety data for evidence of study-related adverse events;
- Adherence to the protocol;
- Factors that might affect the study outcome or compromise the trial data (such as protocol violations, losses to follow-up, etc.).
- Review the achievement of enrollment benchmarks

The SMC will receive monthly reports via email for review and comments. The SMC will be contacted directly via email (and possibly via teleconferencing) for any event or situation that impacts participant safety throughout the study and specified interventions or study participation will be suspended or terminated dependent on the response of the SMC.

The study will undergo review at least annually by the SMC. The SMC will review information on accrual, baseline characteristics, conduct of the study (including premature study discontinuations and premature study treatment discontinuations), AEs by treatment arm (including protocol team assessment of relationship to study treatment), virologic failures, and HIV-1 RNA levels over time, and completeness of follow-up.

Safety Pause

Enrollment into the study and treatment injections will be temporarily suspended and the Study Monitoring Committee (SMC), unblinded to treatment assignment, will be asked to review all safety data. Review will include the relation to study treatment of the event(s) thought by the blinded core team to be a primary safety outcome, if any of the following occur:

- a) Two or more participants experience a primary safety outcome measure that is a Grade ≥ 3 AE possibly related to study treatment (as judged by the core team, blinded to treatment arm); or
- b) One or more participants experience an SAE possibly related to study treatment (as judged by the core team, blinded to treatment arm).

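### Read alone, section 8.3.3 lets a related Grade 1–2 laboratory abnormality that is not clinically significant go unreported as an AE, against section 8.2.11 and the secondary safety endpoint

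*Combined protocol and SAP*

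**What the plan says.** Two sections state when a laboratory value becomes an AE.

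- Section 8.2.11 (Laboratory Evaluations) has the investigator judge each out-of-range result for clinical significance and relatedness. Confirmed abnormal values judged "clinically significant and/or related to a study intervention must be reported as AEs, regardless of grade". Relatedness alone is enough.
- Section 8.3.3 (Clinical Laboratory Changes) says a value is considered an AE if it is an abnormal change from baseline and clinically significant for that participant. The next bullet says: "Generally, Grade 1 and Grade 2 laboratory findings need not be reported as AEs unless deemed clinically significant by the Investigator (or designee". Relatedness appears in neither bullet.

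For signs and symptoms there is one rule (section 8.1): "All signs or symptom, definitely, possibly, or probably related to study interventions will be recorded, regardless of grade".

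The secondary safety endpoint (section 1.1 and section 3) is any related AE of Grade 1 or higher through Day 168. It names laboratory toxicities and sets no clinical-significance condition. Section 9.3.8 tabulates related AEs by grade, and also "All treatment-related AEs with severity Grade 1 or greater", by system organ class and preferred term. The safety committee reviews "AEs by treatment arm (including protocol team assessment of relationship to study treatment" (section 10.1.6).

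**The concern.** A coordinator holding a Grade 1 or 2 result that the investigator calls possibly related but not clinically significant gets two answers: report it under 8.2.11, or generally do not under 8.3.3. No text says which section governs. Someone following 8.3.3 would not class the result as an AE. The secondary endpoint, the section 9.3.8 tables and the by-arm AE review all count AEs, so the result would be absent from each.

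Two named components of one endpoint would then be captured by different rules: related symptoms always, related low-grade laboratory toxicities only if clinically significant. In a first-in-human study whose main purpose is safety, such low-grade laboratory signals should be captured consistently.

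**Working it through.** **Step 1: one case under each rule.** Take a confirmed Grade 1 or 2 abnormality, possibly related, not clinically significant.

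- 8.2.11: must be reported as an AE.
- 8.3.3: generally need not be.
- 8.3.1 (AE definition): covers abnormal laboratory findings that are new or worse than baseline, with no clinical-significance condition.
- 8.3.3, earlier text: all on-study AEs are to be documented whatever their relationship to treatment.
- 8.3.4: related AEs of Grade 1 or higher go into the database. A participant with a related "Grade 1 or 2 AE or lab toxicity that occurs following a vaccine/placebo injection" is to be discussed with the study team, but the sentence requiring documentation speaks of AEs.
- Secondary endpoint and 9.3.8: counted if classed as an AE.

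Reporting satisfies every line. Not reporting fits only the 8.3.3 laboratory bullets.

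**Step 2: what is not touched.** A clinically significant value is reportable under both sections. Section 8.3.3 says Grade 3–4 laboratory findings should be reported, so the primary endpoint (Grade 3 or higher) stands. The pause rules (10.1.6) depend on Grade 3 or higher events and SAEs.

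**Step 3: the plan's own figures.** Section 9.2.1 uses an exact one-sided 95% upper limit, the 0.95 quantile of Beta(x+1, n−x). For n = 7, x = 0 gives 34.8% and x = 1 gives 52.1%, matching the stated 35% and 52%.

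**Step 4: size of one omission, conditionally.** The documents give no rate of related Grade 1–2 laboratory values, so only a conditional effect can be shown.

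- The composite changes only if the participant has no other related AE. If a share p of vaccinees has one, independently of the laboratory finding, the chance of a change is 1 − p.
- Assumed range for p: 30% to 90%, so 1 − p runs from 70% to 10%. One reference point is malaise in 7 of 15 vaccinees (47%) in the earlier three-dose study in section 2.2.4, giving 53%. That is a single symptom and is not stated to be treatment-related there. Local reactions are also expected (section 2.3.1), so p could well be higher and a change less likely.
- When the composite does change, it moves by 1/7 = 14.3 points in an arm, or 1/21 = 4.8 points over the 3 × 7 = 21 vaccinees.
- Illustration at 47%: 7 × 0.467 = 3.3 per arm and 21 × 0.467 = 9.8 pooled. An arm would go from 4/7 to 3/7 (57.1% to 42.9%; upper limit 87.1% to 77.5%). The pooled figure would go from 11/21 to 10/21 (52.4% to 47.6%; upper limit 71.4% to 67.2%).

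The preferred-term row for that finding loses the participant even when the composite does not change, unless another AE already puts them in that row.

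**The case against.** The strongest reply is that the plan as a whole already settles the matter. Section 8.2.11 says must; 8.3.3 says only generally. A specific obligation is normally read as the exception to a general default, so omission needs staff to disregard a mandatory rule. The 8.3.3 bullet on clinical significance gives a sufficient condition and does not say that other changes are not AEs. The AE definition, the documentation rule and the database criterion point the same way. The protocol team reviews safety data monthly. The value itself also survives: Grade 2 and higher values are recorded (8.2.11), clinical laboratory data enter the database (10.1.9.1), and 8.3.4 lists laboratory safety assessments alongside adverse experiences.

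Most of this stands. It shows the intent, and it means that omission is allowed only by 8.3.3 read in isolation. It does not remove the need for an edit. The database criterion applies to events already classed as AEs, which is the step in doubt, and a stored value without AE status is in neither the endpoint nor the AE tables.

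A reader might infer that the gap covers every related Grade 1–2 value, including a Grade 2 dose-limiting finding, since section 8.3.4 says "Hematologic dose-limiting toxicity will be defined as any confirmed toxicity" of Grade 2 or higher not clearly due to another reversible cause. The documents do not support that. A related value judged clinically significant is reportable under both sections, and a confirmed dose-limiting finding is an unlikely candidate for being called not clinically significant.

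**Conclusion.** The inconsistency is real and minor. It concerns confirmed Grade 1–2 laboratory abnormalities judged at least possibly related but not clinically significant. Section 8.3.3 is the section to bring into line, because the rest of the plan treats such findings as countable.

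The effect on results is probably small and cannot be estimated from the documents. The figures in the working rest on an assumed p, on independence, and on at least one omission occurring. It would go too far to say that the plan directs the omission or that laboratory data are lost: only the AE status of the result is in doubt.

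**What to change.** In the 8.3.3 bullet on Grade 1 and Grade 2 laboratory findings, insert after the clinical-significance condition: *or at least possibly related to study treatment*. Add the same trigger to the preceding bullet, so that an abnormal change from baseline is considered an AE if it is clinically significant or at least possibly related. No new database criterion is needed, since related AEs of Grade 1 or higher already qualify under 8.3.4.

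Any check of post-vaccination results already collected should use relatedness judgements made blinded to arm: either made before the unblinding that follows the last participant's Day 28 visit and second leukapheresis (9.2.1.4), or made by staff who remain blinded. Late participants' Day 56 and Day 70 results can fall after that unblinding, so they would need the second route.

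The cost is two phrases and a desk check. The schedule (1.3) has 5 blood counts, 4 safety chemistries and 1 urinalysis per participant after vaccination: 10 × 24 = 240 panels. Three CD4 panels each add 3 × 24 = 72, giving 312. Section 8.2.11 already calls for a relatedness judgement on out-of-range values, so the check is mainly a comparison of those judgements with the AE records. No new visit, sample or table is required.
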